### **G3 Analysis Plan and Statistical Methods**

We are studying D-mannose in postmenopausal women with a history of rUTI on VET. We will plan for an intent to treat analysis with an additional per protocol analysis likely.

For our primary outcome of the RCT, we will calculate the cumulative incidence of symptomatic culture-proven UTIs. If we have loss to follow-up, we will use the Kaplan-Meier method to calculate the cumulative incidence by arm (i.e., 1.0 - survival). We will compare the cumulative incidence between arms by chi-squared tests, Fisher's exact tests, or log-rank tests, as appropriate. Although women will be randomized into the two arms, we will compare their distributions of potential confounding variables by calculating group-specific means and proportions, as appropriate. If these differ by an appreciable degree, we will calculate adjusted associations, using logistic or Cox proportional hazards regression, as appropriate.

We will calculate the incidence of side effects and discontinuation as the number of women in the D-mannose +VET arm who experience these events during follow-up divided by the number of women in the D-mannose +VET arm. 95% confidence limits will be calculated by normal approximation or the Clopper-Pearson exact method, as appropriate.

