Alton et al found the frequency of mannose adverse effects is dose dependent, with only 10% of their study subjects experiencing gastrointestinal disturbances and bloating at 0.15 g mannose/kg body weight [17]. Using the numbers from Alton's study, if a study participant weighs 100 pounds then the participant would have a 10% chance of experiencing gastrointestinal side effects if a mannose dose of 6.8 grams were used, which is a much larger dose than the 2 grams per day in this study protocol. This same study also found that regardless of the mannose dose used in their study (which ranged from 0.1-0.25 g mannose/kg body weight), participants' blood glucose levels were stable and within the normal physiologic range. This study protocol uses a smaller dose of D-mannose than Alton's study: for a 100 pound study participant, the 2 grams/day total dose would equal 0.044 g D-mannose/kg body weight. In order to exceed the maximum D-mannose dose in Alton's study (where the blood glucose level was still not affected), a participant in our study would have to weigh less than 18 pounds, which is considerably less than the weight of a post menopausal woman.

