## 2.f Risks and Benefits

D-mannose is a nutraceutical sold over the counter solely for the prevention of UTI. It falls under the category of dietary supplements regulated by FDA under the Dietary Supplement Health and Education Act of 1994 (DSHEA) [24]. This is a different set of regulations than the regulations used for conventional food and drug products [24]. Risks associated with D-mannose use are believed to be mainly related to gastrointestinal side effects (bloating, loose stool, and diarrhea). Other possible side effects can include but are not limited to hypersensitivity or allergic reactions (acute skin or pulmonary changes). These side effects would be the same for subjects enrolled in this study as for patients not enrolled in this study that we recommend D-mannose prophylaxis to on a daily basis. Other potential risks of the study include participants may feel uncomfortable or be inconvenienced by filling out study related papers. They may prefer to obtain treatment for UTI-like symptoms from an urgent care or other outside provider. However, all rUTI patients in our office (no matter if enrolled in the study or not) are instructed to call our office when they experience UTI-like symptoms since our clinical practice is to obtain (when possible) urine cultures prior to initiating treatment and to have our patients followed primarily through our office for their urinary tract infections.

A potential benefit is the decreased incidence of rUTI among patients randomized to D-mannose in the randomized, controlled trial portion of the study or patients in the observational arm of the study. Otherwise, benefits for the participant are no different than if they were recommended D-mannose as part of their routine clinical care as a patient without being enrolled in the study. There is a global benefit of increased knowledge surrounding the utility of non-antibiotic prophylaxis for rUTI.

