### **3.e Subject Compliance Monitoring**

All participants will be asked to complete a simple weekly study diary. The 90 days of the study will be divided into 12 full weeks and 1 partial week for a total of 13 weeks of the diary. In the diary, one of the questions asked for each week of the study is number of doses missed each week. This study will use a text message service through the REDCap (Research Electronic Data Capture) database. During the 90 day study period, all study participants in both the RCT and Observational arms will receive text message reminders to complete their study diary for the week on study days 7, 14, 21, 28, 35, 42, 49, 56, 63, 70, 77, 84, and 90. This same text message will ask patients if any new symptoms were experienced in the past week and request a “Yes” or “No” response via text message. Study participant responses will automatically be entered in the REDCap (Research Electronic Data Capture) database for this study. If the study participant sends a “Yes” response by text message a member of the research team will contact the patient to follow up for more information about the symptoms. If they declined text messaging when enrolling in the study, the study participant will receive periodic phone calls with reminders to complete their study diary. The subject will be instructed to bring their study diary to each appointment.

Six weeks into the study, each study participant will receive a phone call from a member of the research team. During this phone call questions referencing compliance with completing the study diary, taking study medications as prescribed, if they have been treated for a UTI by anyone outside of our office during the study period, side effects noted, and if they have any questions to be answered will all be addressed.

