### **3.c Definitions of Adverse Events**

Adverse events will include medication side effects including gastrointestinal upset symptoms such as nausea, vomiting, flatulence, diarrhea, dyspepsia, and abdominal pain. Other medication side effects may include rash or itching.

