### **3.d Classification of Events**

#### **i Severity**

All expected adverse events are of mild severity.

For this study, the following standard adverse event (AE) definitions are used:

Adverse event: Any unfavorable and unintended sign, symptom, or disease temporally associated with the use of a medical treatment or procedure, regardless of whether it is considered related to the medical treatment or procedure.

Serious Adverse Event (SAE): Any AE related to the study drug that results in any of the following circumstances: death, life-threatening, event requiring inpatient hospitalization or prolongation of existing hospitalization, persistent or significant disability/incapacity

AEs are graded according to the following scale:

Mild: An experience that is transient and requires no special treatment or intervention. The experience does not generally interfere with usual daily activities.

Moderate: An experience that is alleviated with simple therapeutic treatments. The experience impacts usual daily activities.

Severe: An experience that requires therapeutic intervention. The experience interrupts usual daily activities. If hospitalization (or prolongation of hospitalization) is required for treatment of something related to the study drug, it becomes a SAE.

The study uses the following AE attribution scale:

Not related: The AE is clearly not related to the study procedure (i.e., another cause of the event is most plausible and/or a clinically plausible temporal sequence is inconsistent with the onset of the event).

Possibly related: An event that follows a reasonable temporal sequence from the initiation of study procedures, but that could readily have been produced by a number of other factors.

Related: The AE is clearly related to the study procedures.

---

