## ii      **Expectedness**

Less common: gastrointestinal upset symptoms (such as nausea, vomiting, flatulence, diarrhea, constipation, dyspepsia, and abdominal pain)

Rare: Rash or itching with medication.

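### Side-effect incidence is planned for the D-mannose + VET arm only, with no by-arm table, although the symptom contacts also cover the VET-alone arm

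*Combined protocol and SAP*

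**What the plan says.** G3 (Analysis Plan and Statistical Methods) takes the incidence of side effects and of discontinuation "as the number of women in the D-mannose +VET arm who experience these events during follow-up", over the number of women in that arm. The interval is for a single proportion, by normal approximation or Clopper-Pearson. G3 plans no such figure for VET alone and no comparison.

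The matching secondary aim in C2 is descriptive: the side effects of D-mannose, and discontinuation because of them. The central hypothesis in A2 goes further. It calls D-mannose tolerable in a sentence that compares its use on top of VET with VET alone.

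The contacts that pick up symptoms are not confined to the D-mannose arm. E3 3.e says "all study participants in both the RCT and Observational arms will receive text message reminders", and the same text asks about new symptoms. Under E3 3.e and F2 every participant also gets a six-week call that covers side effects. F3 3.a adds a three-month visit with a chart review for unreported adverse events.

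F3 3.d defines an adverse event "regardless of whether it is considered related to the medical treatment or procedure" and then sets three attribution levels: "The study uses the following AE attribution scale" (not related, possibly related, related).

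**The concern.** Gastrointestinal upset, rash and itching are non-specific, and some women would report them over 90 days without D-mannose. A single-arm proportion mixes that background with whatever D-mannose adds. If the rate is low this hardly matters, because the whole rate is then a small upper limit on the added burden. If it is not low, the reader has no reference level, although a concurrent randomised group is contacted on the same schedule.

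What is at stake is the reading of a secondary safety result and the weight that the word tolerable can carry.

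**Working it through.** **Inputs.** 60 women per RCT arm (G1). No symptom rate for either arm is given, so all counts below are assumed. For orientation, D2 cites an earlier study "with only 10% of their study subjects experiencing gastrointestinal disturbances and bloating at 0.15 g mannose/kg body weight" and puts this trial's dose at 0.044 g/kg for a 100-pound woman. The ratio is 0.15/0.044 = 3.4, so the cited dose is about 3.4 times higher. F3 3.d also lists the symptoms as "Less common: gastrointestinal upset symptoms". Low scenarios therefore come first.

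**Step 1: what G3 would report.** Clopper-Pearson limits for x events in n = 60 are the 2.5% quantile of Beta(x, n - x + 1) and the 97.5% quantile of Beta(x + 1, n - x).

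| Events | Rate | 95% CI |
|---|---|---|
| 3/60 | 5.0% | 1.0 to 13.9 |
| 6/60 | 10.0% | 3.8 to 20.5 |
| 12/60 | 20.0% | 10.8 to 32.3 |

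**Step 2: what a by-arm table would add.** Risk difference d = p1 - p2, with Newcombe limits built from the Wilson limits (l, u) of each arm:

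- lower = d - sqrt[(p1 - l1)² + (u2 - p2)²]
- upper = d + sqrt[(u1 - p1)² + (p2 - l2)²]

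For 12/60 vs 6/60 the Wilson limits are 11.8 to 31.8% and 4.7 to 20.2%. The difference is 20.0 - 10.0 = 10.0 points, with limits -3.0 and 22.9.

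| D-mannose + VET vs VET alone | Difference (points) | 95% CI |
|---|---|---|
| 3/60 vs 3/60 | 0 | -9.3 to 9.3 |
| 6/60 vs 3/60 | 5 | -5.2 to 15.7 |
| 6/60 vs 6/60 | 0 | -11.5 to 11.5 |
| 12/60 vs 6/60 | 10 | -3.0 to 22.9 |

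**Step 3: how much this can settle.** In every row the interval contains zero (the whole D-mannose rate could be background). In every row its upper limit also exceeds the whole D-mannose rate (none of it need be background): 9.3 against 5, 15.7 against 10, 11.5 against 10, 22.9 against 20. The table supplies a reference level, not a separation of the two sources.

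**Step 4: is a crude difference a fair contrast?** G1 assumes UTI in 20% of women on D-mannose and 45% on VET alone. Two features of the plan then act unequally on the arms.

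- F2 describes participants who finish early because of a culture-proven UTI. Under the G1 rates that would shorten symptom follow-up more often in VET alone, which lowers its count.
- B1 calls gastrointestinal upset common with antibiotics and cites side effects in 27.2% of women on nitrofurantoin prophylaxis. If that rate carried over to acute treatment (an assumption, for illustration only), the excess of treated UTIs would add (0.45 - 0.20) × 27.2% = 6.8 points of symptoms to VET alone. That is more than the 5-point difference in the second row.

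The two effects pull in opposite directions, so the sign of the net bias is unknown. A usable table must show follow-up time and a version free of post-UTI events.

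**The case against.** The strongest defence is that G3 matches its aim. C2 asks only for a description of D-mannose side effects, and D-mannose is the only study drug (D1). F3 3.c speaks of medication side effects ("Adverse events will include medication side effects including gastrointestinal upset symptoms"), so the numerator can be read as attributed events, for which a VET-alone rate means little. In addition, F3 3.b sends compiled adverse events to a DSMB that includes a biostatistician, so safety review is wider than one proportion. Much of this stands: the planned proportion is legitimate and should stay. But the DSMB text does not specify presentation by arm. Attribution would be made in a trial without placebo, so an attributed rate does not replace a control rate.

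A second objection is that the comparison is imprecise and tilted by differential UTI. Both parts are right. They limit what the table can claim and shape how it should be built, but they are not reasons to leave the control-arm data untabulated.

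A reader might also infer that the side-effect definition is contradictory. E2 2.f names "gastrointestinal side effects (bloating, loose stool, and diarrhea", terms not all repeated in F3, and F3 3.e words the weekly question differently from E3 3.e. The documents do not support a finding there. The symptom lists are openly illustrative, the wording difference may be loose drafting, and the attribution level for G3 is missing detail rather than an error. The differing statements on blinding in E3 3.g and G2 are a separate matter.

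**Conclusion.** The point holds as a modest improvement to consider. G3 leaves the VET-alone symptom data unused, so a D-mannose rate that is not low would stand without a randomised reference when tolerability is judged. At 3/60 the comparison adds little. At 6/60 or 12/60 it gives useful context, with an interval reaching about 11 to 13 points either side in the 6 vs 6 and 12 vs 6 cases.

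A reader might infer that a by-arm table would show whether the observed rate is mostly background. It would not: in all four assumed scenarios the interval is compatible with all of the rate being background and with none of it. Nor does the gap undermine the trial, since the primary result and the 60 per arm are unaffected.

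The conclusion rests on assumed counts, on full arms of 60, and on symptom questions being alike in both arms. The last cannot be checked, because the forms listed in K3 are not in the documents.

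**What to change.** Keep the planned D-mannose + VET proportion and the single-arm discontinuation rate. Add to G3:

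- a descriptive table by RCT arm of adverse events as F3 3.d defines them, whatever their attribution, with possibly related and related events shown separately;
- the risk difference (D-mannose + VET minus VET alone) with a 95% CI, preferably by the Newcombe method, since the Wald interval is unreliable at counts as low as 3/60;
- follow-up time per arm, and a second version limited to events before the first treated UTI;
- a statement that the comparison is open-label, without placebo and imprecise, so that it gives context and cannot by itself separate background from D-mannose effect.

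The cost is a short addition to G3 and one extra table with wide intervals. No new contacts are needed on the plan's own description. The team must confirm that the symptom items on its diaries, call forms and three-month forms match across the two RCT arms.

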### ***C2 Secondary Aims***

There are multiple secondary aims of this study:

- To compare the incidence of symptomatic, culture-proven urinary tract infections caused by all uropathogens potentially susceptible to D-mannose therapy in women receiving D-mannose and the control group. We will also compare these findings to the incidence of symptomatic, culture-proven urinary tract infections caused by uropathogens susceptible to D-mannose therapy in the absence of vaginal estrogen therapy (observational arm).
- To describe the side effects of D-mannose and determine the incidence of discontinuation of therapy due to side effects.
- To compare the cumulative incidence of symptomatic, culture-proven urinary tract infections between women receiving prophylactic D-mannose treatment alongside vaginal estrogen therapy versus women receiving prophylactic D-mannose treatment whom are not on vaginal estrogen therapy (observational arm).
- To gain information to use in designing future rUTI studies.

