### ***F2 Schedule of Measurements***

During the clinical visit where the participant is enrolled, she will be asked to complete a form with study-related questions. A urine specimen or other labs may be ordered as part of routine clinical practice at this visit. No additional specimens will be collected for this study except for those clinically indicated.

If a participant is in the Observational arm, then they will receive a phone call approximately one week after study enrollment to confirm if D-mannose powder or capsules were purchased. They will also be asked what brand was purchased and confirm they were able to start the D-mannose on the planned study day 1. If there are delays in the participant's purchasing and receiving of their D-mannose then the date of study day 1 will be adjusted accordingly.

Participants will be expected to complete a weekly paper study diary. All participants that agree to receive text messages will receive a weekly text message reminder to complete their weekly study diary. Text messages will be sent at a standardized time on study days 7, 14, 21,

---

28, 35, 42, 49, 56, 63, 70, 77, 84, and 90. This same text message will ask patients if any new symptoms were experienced in the past week and request a “Yes” or “No” response via text message. Study participant responses will automatically be entered in the REDCap (Research Electronic Data Capture) database for this study. If the study participant sends a “Yes” response by text message a member of the research team will contact the patient to follow up for more information about the symptoms. If they declined text messaging when enrolling in the study, the study participant will receive periodic phone calls with reminders to complete their study diary. The subject will bring their study diary to each appointment.

Six weeks into the study, each study participant will receive a phone call from a member of the research team. During this phone call questions referencing compliance with completing the study diary, taking study medications as prescribed, if they have been treated for a UTI by anyone outside of our office during the study period, side effects noted, and if they have any questions to be answered will all be addressed.

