## **G   Statistical Plan**

### ***G1   Sample Size Determination and Power***

We based our sample size estimate on assumptions for our primary aim, as this is the most important aim for providing information to support future recommendations and studies aimed at individualized patient care. The first published study on D-mannose was a RCT that showed 14.6% of rUTI patients develop another UTI while on treatment [9]. To be conservative in our sample size calculations, we assume 20% of patient on D-mannose will develop a UTI during the three-month treatment period. Very few studies have stated the percent of rUTI patients that develop another UTI while on vaginal estrogen therapy [27-29]. Due to the range of the published values, an average of these numbers was taken to arrive at an assumption that 45% of patients on only vaginal estrogen therapy will develop another UTI during the treatment period. We also accounted for a 10% dropout rate during the study period. Using these numbers to determine sample size, we calculated 60 patients would be needed per RCT arm for a total of 120 patients in the RCT. We recognize that our power for secondary aims is lower; however, we included these to begin to explore these other areas that are fundamental for understanding the underlying mechanism of D-mannose and how it works with rUTI. We have decided to also enroll 60 patients in the Observational arm of the study.

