### **G4 Missing Outcome Data**

Missing data and patterns will be assessed monthly by the data manager. Remedial measures, including retraining of staff, will be used as needed to minimize missing data.

We plan for an intent to treat analysis. In doing this, study participants that are lost to followup will be presumed to not have an acute urinary tract infection from the time of last contact with the study participant.

We will additionally have a per protocol analysis.

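### G3's whole-arm denominator for side effects and discontinuation makes no allowance for incomplete follow-up or women who never take a dose, so the side-effect rate is biased modestly downward (minor)

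*Combined protocol and SAP*

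**What the plan says.** C2 lists as a secondary aim "To describe the side effects of D-mannose and determine the incidence of discontinuation of therapy due to side effects". G3 gives the estimator for both rates: the women in the D-mannose plus vaginal estrogen arm "who experience these events during follow-up divided by the number of women in the D-mannose +VET arm". For precision it adds: "95% confidence limits will be calculated by normal approximation or the Clopper-Pearson exact method, as appropriate".

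For the primary outcome, the same section allows for incomplete follow-up: "If we have loss to follow-up, we will use the Kaplan-Meier method to calculate the cumulative incidence by arm". The rule in G4 (also in E2, 2.h) is likewise about infection: "study participants that are lost to followup will be presumed to not have an acute urinary tract infection". Neither is extended to side effects or discontinuation.

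On analysis sets, G3 says "We will plan for an intent to treat analysis with an additional per protocol analysis likely". G4 then treats the per-protocol analysis as planned, but its membership is not defined and it is not tied to tolerability. No treated or safety set appears anywhere. On expected losses, G1 says "We also accounted for a 10% dropout rate during the study period".

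**The concern.** The numerator requires that an event was observed. The denominator requires only assignment to the arm. Three kinds of women can sit in the denominator with follow-up that is short or empty:

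- Women lost to follow-up with no earlier report and no retrieved data.
- Women who end early. F2 describes participants completing the study early after a culture-proven UTI.
- Women who are randomised but never take a dose. The envelope is opened after enrolment and consent (E2, 2.e), while study day 1 can fall later, once four weeks of vaginal estrogen are complete (E2, 2.d). The F2 call to "confirm they were able to start the D-mannose on the planned study day 1" is described for the Observational arm only.

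Tolerability is part of the central hypothesis in A2, and B1 says side effects and discontinuation must be assessed before D-mannose can be recommended as standard treatment. An estimator that leans towards the favourable answer matters for that aim, and its confidence limits carry the same lean.

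**Working it through.** **Inputs.** From G1: 60 women per arm, 10% dropout (0.10 × 60 = 6 women), and 20% with a UTI on D-mannose. The documents give no expected side-effect rate at the trial dose. The illustrative 10% is the figure B1 quotes for a higher mannose dose, so event counts from 3 to 15 of 60 are also shown. The number never dosed is not given.

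**The plan's own figure.** G1 states neither alpha nor power. Assuming two-sided 0.05 and 80% power without continuity correction, with 45% versus 20% (mean 0.325):

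n = [1.960 × √(2 × 0.325 × 0.675) + 0.842 × √(0.45 × 0.55 + 0.20 × 0.80)]² / 0.25² = 53.9, so 54 per arm.

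54 / 0.90 = 60, which matches G1.

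**Step 1: 6 women contribute no information at all.** Compare x/60 with x/54, with Clopper-Pearson 95% limits where shown:

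- 3 events: 5.0% (1.0 to 13.9) against 5.6% (1.2 to 15.4)
- 6 events: 10.0% (3.8 to 20.5) against 11.1% (4.2 to 22.6)
- 12 events: 20.0% against 22.2%
- 15 events: 25.0% against 27.8%

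The ratio is always 54/60 = 0.90. With 6 events and 3 to 12 uninformative women, the alternative runs from 6/57 = 10.5% to 6/48 = 12.5%.

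**Step 2: losses spread over the 90 days and unrelated to tolerability.** Assume constant hazards, with h = −ln(1 − true risk) and g = the total exit hazard over 90 days. The expected crude proportion is h/(h + g) × [1 − exp(−(h + g))].

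- 10% true risk, 10% dropout: h = g = −ln 0.90 = 0.105, giving 0.5 × (1 − 0.81) = 9.5%.
- Adding 20% who end early because of UTI: g = 0.105 − ln 0.80 = 0.329, giving (0.105/0.434) × (1 − 0.648) = 8.5%.

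The shortfall is 0.5 points from dropout alone and about 1.5 points with early ending after UTI.

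**Step 3: worst-case bound.** If all 6 lost women had stopped unreported, 3 recorded stops become 9/60 = 15.0% (7.1 to 26.6). If all 6 had unreported side effects, 6 recorded events become 12/60 = 20.0% (10.8 to 32.3).

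**Step 4: dropping lost women is not a safe remedy.** If 1 of the 6 recorded side effects belongs to a woman later lost, completers only give 5/54 = 9.3%. If 2 do, they give 4/54 = 7.4%. Both fall below the 10.0% that G3 would report.

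**Step 5: direction for discontinuation.** C2 asks about stopping because of side effects; G3 names discontinuation without that limit. With 3 such stops, a single stop for another reason counted under G3 gives 4/60 = 6.7%, already above the 5.6% in Step 1. The wording can therefore outweigh the denominator effect.

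**The case against.** The strongest reply is that the plan works hard to capture these events. Diaries and symptom texts are weekly, with a phone call after any positive answer, and there is a six-week call about side effects and taking the medication (E3, 3.e). Women who withdraw are asked for an exit survey that covers why they left (E2, 2.i), and lost women are sought by phone or mail. RCT women are handed the powder, record missed doses and return what is unused, so never starting may be rare. The rates are descriptive, come from one arm and carry no decision rule. A crude proportion of the assigned arm is transparent and fits the intent-to-treat plan.

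Most of this stands and limits the size of the point. It does not remove it: retrieval is voluntary and fails for women who cannot be reached, and nothing in G3 says how they are handled for these two rates.

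A reader might infer three stronger things that the documents do not support:

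- That every lost woman counts as tolerating D-mannose. An event reported before loss stays in the numerator.
- That the formula can only lower both rates. For discontinuation, G3's broader wording could raise the rate.
- That a gap such as 5% against 15% is to be expected. It requires every lost woman to have stopped unreported, and G1's dropout is not the same as loss without any information.

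**Conclusion.** The point holds as a minor one. G3's estimator treats unobserved women as event-free and has no treated set, so the side-effect rate is biased downward. At the planned dropout the shift is about 0.5 to 1.1 points on a 10% rate, and about 1.5 points if 20% also end early because of UTI. That is small beside 95% limits of 3.8% to 20.5% at 6 of 60. The 0.5 and 1.5 point figures rest on constant hazards and uninformative loss; the 1.1 point figure assumes that 6 women contribute nothing. If women who stop because of side effects are also the ones who stop replying, the shift could be larger; the documents give no basis for its size, so only a bound can be stated. For discontinuation the net direction cannot be determined until G3 says which stops count. The primary UTI comparison is unaffected.

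**What to change.** Amend the tolerability paragraph of G3:

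- **Denominator.** For these two rates, use women who took at least one dose of D-mannose. Keep all randomised women for the UTI analysis.
- **Event.** Count discontinuation because of side effects, as in C2, and report other stops separately.
- **Estimate.** Report the crude x/n together with the number lost or ended early. Add a Kaplan-Meier 90-day incidence, the method G3 already names for UTI, censoring at last contact or end of follow-up and keeping earlier events. Do not simply drop lost women.
- **Bound.** Censoring assumes uninformative loss and so does not remove informative loss. Add one bound in which lost women count as having stopped because of side effects.

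The cost is a few sentences, plus first-dose, onset and stop dates. Week-level dates from the weekly diary and text would suffice. The forms are attachments not reproduced in the document, so whether these dates are already collected cannot be confirmed. No extra patients or visits are needed. The downside is slightly less favourable rates with somewhat wider limits.
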